6.4.5.3.3. Collection of Urine

In an effort to reduce experimental variability, a urine sample will be collected as soon as possible after the participant enters the clinic after a fast since midnight. Urine will be measured into aliquots with and without preservative (antioxidants). Samples will be frozen immediately after aliquoting at -80° C and batch shipped to the GIC.

6.4.5.4. Measurements

6.4.5.4.1. Blood

- Blood samples collected for Complete Blood Counts (CBC) with differentials will give:
 - White blood cell count per volume of blood
 - White blood cell differentials (neutrophils, lymphocytes, monocytes, eosinophils, and basophils)
 - Red blood cell count per volume of blood
 - Hemoglobin
 - Hematocrit (percent red blood cells per volume of blood)
 - Platelet count (number of platelets per volume of blood)
 - Mean corpuscular volume (average size of red blood cells)
 - Mean corpuscular hemoglobin (average amount of oxygen-carrying hemoglobin inside a red blood cell)
 - Mean corpuscular hemoglobin concentration (average concentration of hemoglobin inside a red cell)
 - Red cell size distribution
- P100 plasma will be prioritized toward proteomics and/or metabolomics analyses that require high quality plasma where the analytes of interest are not predefined or known.
- EDTA plasma will be prioritized toward analysis of known biomarkers or hypothesis driven biomarker analyses where it is previously determined, or reasonably speculated, that EDTA plasma will serve as an excellent source to measure the analyte of interest.
- Serum will be prioritized toward analysis of known biomarkers or hypothesis driven biomarker analyses where it has been previously determined, or reasonably speculated, that serum will serve as the best source for analyte measurement.
- DNA from whole blood will be used for fine-mapping genotyping analyses, evaluating SNPs or sequencing of regions/genes as defined by other large studies, such as COPD-Gene that focus on identification of genetic markers associated with COPD.
- RNA will be used for transcriptomics of mRNA/microRNA or for analyses focused on single-gene expression. High quality is paramount to the success of these efforts.

6.4.5.4.2. Urine

- For women of child-bearing age, at those sites where urine tests are acceptable, urine will be used for pregnancy determination as measured using the analyte, human chorionic gonadotropin (hCG).
- Urine will be prioritized toward proteomics and/or metabolomics studies and/or hypothesis-based studies to define pathogenic features of COPD.
- Urine will be analyzed for cotinine to assess participants' smoking status.

6.4.5.5. Human Subjects' Protection and Risks

6.4.5.5.1. Blood draws

- Veins vary in size from one participant to another and from one side of the body to the other. Obtaining a blood sample from some people may be more difficult than from others.
- Other risks associated with having blood drawn are slight but may include:
 - Excessive bleeding
 - Fainting or feeling light-headed
 - Hematoma (blood accumulating under the skin)
 - Infection (a slight risk any time the skin is broken)
 - Discomfort related to needle stick
 - Rarely, injury to adjacent structures

6.4.5.5.2. Urine

- Urine collection is a benign procedure not associated with risk to the participant.
- Pregnancy testing may reveal unknown pregnancy, which will need to be appropriately communicated to the participant following strict confidentiality protocols.

6.4.6. Sputum Induction

6.4.6.1. Background and rationale

Sputum induction provides an opportunity to directly measure biomarker activity within the lung. These biomarkers are suggestive of disease mechanisms and include mucociliary clearance (e.g., mucins, regulators of airway surface liquid), inflammation (e.g., cell counts, cytokines, and chemokines), infection (e.g., microbiome), oxidative stress, and protease/anti-protease activity.

SPIROMICS will analyze and process induced sputum using the "whole sputum" method as opposed to the "select sputum" method, which involves manually removing sputum plugs from the sample. "Whole sputum" is defined as the raw, unaltered, total expectorated secretions collected from the participant at the conclusion of the induction. It contains whatever secretions were expectorated by the participant.

Sputum induction is first attempted at the baseline study visit. If for some reason the sample is not collected at baseline, additional attempts to collect the sample will be made a subsequent

visits. Participant must produce enough sputum to complete a cytospin slide in order for the collection to be considered “complete.”

6.4.6.2. Inclusion/exclusion specific to procedure

6.4.6.2.1. Inclusion criteria

There are no additional inclusion criteria.

6.4.6.2.2. Exclusion criteria

- Participants with a known intolerance to albuterol or salmeterol
- Participants with a known history of poor outcomes with sputum induction
- Participants with a post-bronchodilator FEV₁ of <35% during screening

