5.3.1.2. Temporary exclusion criteria

Temporary exclusion criteria are events, diseases, or treatments that require a waiting period to elapse before a participant can be screened for SPIROMICS. In addition, these criteria should be applied when scheduling the Years 1, 2, and 3 visits.

- Participants who present with a pulmonary exacerbation, either solely participant-identified or that has been clinically treated, in the last six weeks can be rescreened for the study once the six-week window has passed.
- Participants who present with an upper respiratory infection, either solely participant-identified or that has been clinically treated, in the last six weeks can be rescreened for the study once the six-week window has passed.
- Participants who present with current use of acute antibiotics or steroids can be rescreened for the study ≥ 30 days after discontinuing acute antibiotics/steroids. This does not apply to participants who are on chronic prednisone therapy of < 10 mg per day or < 20 mg every other day or participants who are currently on chronic, prophylactic, or suppressive antibiotic therapy.
- Participants who are currently on chronic, prophylactic, or suppressive antibiotic therapy must have started this therapy at least 6 weeks prior to the baseline visit.
- Participants who present with a myocardial infarction or eye, chest or abdominal surgery within six weeks can be rescreened after the six week window has passed. Study coordinators should consult with the site principal investigator prior to rescreening these participants.
- Female participants who present < 3 months after giving birth will be asked to reschedule their visit until three months have passed since the birth.

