6.2. Schedule of Measurements

Table 3. Schedule of Study Measurements

	V1	V2	V3	V4
Physiological Measures				
Pulmonary Function Testing				
Exhaled CO (eCO)	X	X		X
Forced Vital Capacity	X	X	X	X
Slow vital capacity	X	X	X	X
Bronchodilation	X	X	X	X
Forced Vital Capacity	X	X	X	X
Slow Vital Capacity	X	X	X	X
Six minute walk test with continuous pulse oximetry	X	X	X	X
Anthropometric Measurements				
Height	X	X	X	X
Weight	X	X	X	X
Arm Span	X	X	X	X
Waist	X	X	X	X
Hip	X	X	X	X
Neck	X	X	X	X
Seated Blood Pressure	X	X	X	X
MDCT	X	X		
Biospecimen collection				
Blood				
Serum (Two - RT)	X	X		X
Plasma (One - P100)	X	X		X
Plasma (Three - Plasma/DNA w/EDTA and One CBC w/EDTA)	X	X		X
Plasma (One –with citrate)	X	X		X
RNA (One – PAX - Gene)	X	X		
Urine	X	X		X
Induced Sputum	X	X*	X*	X*
Questionnaires				
Medical History	X	X	X	X
St. George’s Respiratory Questionnaire	X	X	X	X
MOT Short Form – 12	X	X	X	X
COPD Assessment Test	X	X	X	X
Modified Medical Research Council (MRC) Dyspnea Scale	X	X	X	X
Sleep questionnaires				
Berlin Questionnaire	X	X	X	X
Pittsburgh Sleep Quality Index	X	X	X	X
Veterans Specific Activity Questionnaire	X	X	X	X
Hospital Anxiety and Depression Scale (HADS)	X	X	X	X
FACIT	X	X	X	X
Questionnaire for Ease of Cough and Sputum Clearance	X	X	X	X

*Sample collection attempted only if initial collection at baseline failed.

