6.4.6.3. Methods

6.4.6.3.1. Instructions prior to commencing procedure

To conduct a sputum induction participants must not eat or drink anything (except water) for at least two hours prior to beginning the induction. Participants must also have been able to perform three reproducible flow-volume curves during the pulmonary function testing portion of the study visit. For participants at risk of bronchospasm, the post-bronchodilator values are acceptable.

Participants should be coached in the proper technique for saline inhalation, coughing, and nasal/oral/pharyngeal cleansing (see MOP 5 – Sputum Induction and Processing for specific instruction).

For induced sputum, if COPD subjects have not had albuterol in the prior 165 minutes then they should be re-dosed with 2 puffs of albuterol. Participants who are non-smokers or smokers without obstruction do not need albuterol for the sputum induction. The investigator should be contacted if a participant reports having asthma and would otherwise not receive albuterol. Please see Section 6.4.1.4 for bronchodilator dosing and re-dosing instructions.

6.4.6.3.2. Instructions for induction:

Induction requires approximately 20 minutes to complete once the participant has begun saline inhalation. Saline concentrations should be adjusted based on whether the participant’s initial FEV₁ post albuterol is less than or greater than 50% predicted. Participants with a post albuterol FEV₁ of > 50% predicted will begin with 3% saline and participants with a post albuterol FEV₁ of < 50% and > 35% predicted will begin with 0.9% saline. Spirometry is repeated during the induction process at one, two, five, and seven minutes (FEV₁ <50% predicted) or two and seven minutes (FEV₁ >50% predicted). Adjustments to the saline concentration can be made if a participant’s FEV₁ falls more than 10% during the course of the induction. Please see MOP 5 for additional details.

6.4.6.3.3. Procedure Termination:

The procedure is terminated 1) if the FEV₁ falls by > 20% at any time point, or 2) if the participant requests that the procedure be stopped, or 3) after three seven-minute inhalation periods have been completed.

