6.4.6.6. Human Subjects' Protection and Risks

6.4.6.6.1. Risks with hypertonic saline

Inhalation of hypertonic saline for sputum induction may result in wheezing, coughing, or chest tightness, particularly in susceptible individuals such as those with asthma. Asthmatic participants will be pre-medicated with albuterol in order to minimize this risk. Spirometry will be evaluated for all participants before induction as well as at prescribed intervals during each of the three levels of hypertonic saline. Participants may also experience transient throat irritation during the hypertonic saline inhalation but this generally resolves post-induction when the participant is provided with a snack and juice or water.

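### The sputum-induction FEV1 exclusion is dated to screening, so a participant at or below 35% predicted at a later re-attempt is not excluded yet has no starting saline (minor safety correction)

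*Protocol*

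**What the plan says.** All references are to the Protocol.

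- **Exclusion.** Section 6.4.6.2.2 excludes from sputum induction anyone with a post-bronchodilator FEV1 "of <35% during screening". It does not say that the percentage is of the predicted value. It separately excludes "Participants with a known history of poor outcomes with sputum induction".
- **Repeat attempts.** The footnote to Table 3 (section 6.2) marks induction at the three visits after baseline: "Sample collection attempted only if initial collection at baseline failed". Section 6.4.6.1 agrees: "If for some reason the sample is not collected at baseline, additional attempts to collect the sample will be made" at later visits.
- **Dosing at induction.** Section 6.4.6.3.2 sets the starting saline from the participant's initial post-albuterol FEV1. Above 50% predicted it is 3%. Those "< 50% and > 35% predicted will begin with 0.9% saline". No concentration is given at or below 35%.
- **Current spirometry.** Section 6.4.6.3.1 requires "three reproducible flow-volume curves during the pulmonary function testing portion of the study visit". Section 6.4.6.6.1 adds: "Spirometry will be evaluated for all participants before induction".
- **Criteria carried forward.** Section 5.3.1.2 says of the temporary exclusions that "these criteria should be applied when scheduling the Years 1, 2, and 3 visits". That list contains no FEV1 limit.

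**The concern.** The exclusion and the dosing rule use the same threshold at different times. The exclusion looks once, at screening. The dosing rule looks at the FEV1 on the day of induction, which may be one, two or three years later. FEV1 decline over three years is one of the study's primary clinical endpoints (section 7.4.3), so the plan itself expects some participants to cross 35% in that time.

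For such a participant, the exclusion list gives no reason to withhold the procedure and the dosing rule gives no way to start it. Staff have to work out for themselves that induction should not go ahead. What is at stake is the clarity of a safety limit for people with severe obstruction who inhale saline. No analysis depends on it.

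**Working it through.** The Protocol has no figure to reproduce on this point. The check is a comparison of the rules, followed by an illustration of whether the gap can be reached.

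**1. When induction can happen.** Table 3 marks induction at baseline and at Years 1, 2 and 3, which is 4 visits. The time point in the exclusion fits 1 of them (baseline), leaving 4 − 1 = 3 that it does not describe.

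**2. What each rule does at a re-attempt, for a participant above 35% at screening.**

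| Current FEV1, % predicted | Excluded by 6.4.6.2.2? | Starting saline in 6.4.6.3.2 |
|---|---|---|
| Above 50 | No | 3% |
| Above 35 and below 50 | No | 0.9% |
| 35 or below | No | None |

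The last row is the mismatch. A value of exactly 35% falls into it even at baseline, because the exclusion is strictly below 35% and the dosing band strictly above.

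**3. Whether another rule closes the gap.**
- The criteria carried to later visits by section 5.3.1.2 set no FEV1 level.
- The reproducible-curves condition in 6.4.6.3.1 concerns test quality and sets no level.
- The spirometry before induction in 6.4.6.6.1 gives staff a current value, but no exclusion is attached to it.
- The stopping rule in 6.4.6.3.3 (a fall of more than 20%) is relative and acts only after inhalation has begun. From 34% predicted it would act below 34 × 0.80 = 27.2%.
- The exclusion for earlier poor outcomes needs an earlier event.

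**4. Whether the gap can be reached (illustration only).** Let s be the screening FEV1 (% predicted), d an assumed decline in percentage points per year, and t the year. Put m = s − d·t, and take the SD of a single measurement as 4.1% of m. The 4.1% is the short-term coefficient of variation in section 6.4.1.1, which was obtained in mild COPD. The decline is not in the Protocol, so a range of 0 to 2 points per year is shown. The chance of measuring below 35% is Φ((35 − m)/(0.041·m)).

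For s = 36 and d = 0: (35 − 36)/(0.041 × 36) = −1/1.476 = −0.68, giving 0.249.

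| s | d | Year 1 | Year 2 | Year 3 |
|---|---|---|---|---|
| 36 | 0 | 0.249 | 0.249 | 0.249 |
| 36 | 1 | 0.500 | 0.763 | 0.930 |
| 36 | 2 | 0.763 | 0.989 | 1.000 |
| 38 | 0 | 0.027 | 0.027 | 0.027 |
| 38 | 1 | 0.094 | 0.249 | 0.500 |
| 38 | 2 | 0.249 | 0.763 | 0.989 |
| 40 | 0 | 0.001 | 0.001 | 0.001 |
| 40 | 1 | 0.006 | 0.027 | 0.094 |
| 40 | 2 | 0.027 | 0.249 | 0.763 |

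Someone just above 35% at screening can plausibly be below it later. The table says nothing about how many such people there are, because the Protocol gives neither the FEV1 distribution near 35% nor the rate of failed baseline collections.

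**The case against.** The strongest reply is that the two rules act as successive checks. A participant below 35% at Year 2 passes the exclusion and stops at the dosing rule, since no starting concentration is authorised. COPD participants are also pre-treated with albuterol if they have had none in the preceding 165 minutes. With FEV1 below 50%, spirometry is repeated at 1, 2, 5 and 7 minutes, and the saline can be adjusted after a fall of more than 10%. This stands as an argument that harm is unlikely. It does not make the exclusion right, because the limit that matters at a re-attempt then has to be inferred from a missing dosing band.

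A second reply is that screening might mean the check before each procedure. The first contact in section 6.1 can be by telephone and yields no FEV1, so the value must come from a clinic visit, and the criterion sits under a procedure-specific heading. The wording is therefore not airtight. But sections 6.1 and 5.3.1.2 use screening for entry to the study, and nothing in the Protocol extends this criterion to later visits.

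A third reply is that MOP 5, to which section 6.4.6.3 refers for detail, may hold a visit-level rule. That is possible and cannot be checked here.

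A reader might infer more: that the plan permits induction below 35%, that staff would proceed without a current FEV1, or that three of four visits measures exposure. The documents support none of these. No saline is assigned at or below 35%, and current spirometry is required. Re-attempts occur only after a failed baseline collection, so the visit count describes the wording and not the number of people at risk.

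**Conclusion.** The point holds as a minor participant-safety correction. The exclusion is fixed at screening, while induction can be attempted up to three years later under a dosing rule with a floor of 35% predicted. A participant who has fallen to 35% or below is neither excluded nor assigned a starting concentration.

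The group should be small. It needs a failed baseline collection, a screening FEV1 not far above 35%, and a later value at or below 35%. Its size cannot be derived from the Protocol. There is no effect on power, endpoints or error rates.

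The conclusion rests on reading screening as entry to the study, as section 6.1 does, and on the Protocol alone. If MOP 5 already applies the limit at each attempt, only the Protocol wording needs to catch up.

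**What to change.** In section 6.4.6.2.2, replace the FEV1 criterion with: *post-bronchodilator FEV1 of 35% predicted or less on the spirometry evaluated before the induction being attempted (baseline or any re-attempt)*.

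Three details of this wording matter:
- *35% or less* meets the dosing floor exactly, so the boundary value is no longer left over.
- *Predicted* supplies the missing reference.
- Tying the value to the spirometry before that induction is safer than tying it to the visit. Section 6.3 lets one visit's procedures spread over 42 days, and section 6.4.1.4 allows induction on a different day from the study spirometry.

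The cost is one phrase, and MOP 5 should be checked for agreement. No measurement is added: section 6.4.6.6.1 already requires spirometry before induction, and section 6.4.1.6 already lists FEV1 as a percentage of predicted. The downside is a few fewer late sputum samples in severe disease, from participants for whom the Protocol gives no starting saline in any case.

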6.4.6.3. Methods

6.4.6.3.1. Instructions prior to commencing procedure

To conduct a sputum induction participants must not eat or drink anything (except water) for at least two hours prior to beginning the induction. Participants must also have been able to perform three reproducible flow-volume curves during the pulmonary function testing portion of the study visit. For participants at risk of bronchospasm, the post-bronchodilator values are acceptable.

Participants should be coached in the proper technique for saline inhalation, coughing, and nasal/oral/pharyngeal cleansing (see MOP 5 – Sputum Induction and Processing for specific instruction).

For induced sputum, if COPD subjects have not had albuterol in the prior 165 minutes then they should be re-dosed with 2 puffs of albuterol. Participants who are non-smokers or smokers without obstruction do not need albuterol for the sputum induction. The investigator should be contacted if a participant reports having asthma and would otherwise not receive albuterol. Please see Section 6.4.1.4 for bronchodilator dosing and re-dosing instructions.

6.4.6.3.2. Instructions for induction:

Induction requires approximately 20 minutes to complete once the participant has begun saline inhalation. Saline concentrations should be adjusted based on whether the participant’s initial FEV₁ post albuterol is less than or greater than 50% predicted. Participants with a post albuterol FEV₁ of > 50% predicted will begin with 3% saline and participants with a post albuterol FEV₁ of < 50% and > 35% predicted will begin with 0.9% saline. Spirometry is repeated during the induction process at one, two, five, and seven minutes (FEV₁ <50% predicted) or two and seven minutes (FEV₁ >50% predicted). Adjustments to the saline concentration can be made if a participant’s FEV₁ falls more than 10% during the course of the induction. Please see MOP 5 for additional details.

6.4.6.3.3. Procedure Termination:

The procedure is terminated 1) if the FEV₁ falls by > 20% at any time point, or 2) if the participant requests that the procedure be stopped, or 3) after three seven-minute inhalation periods have been completed.

6.4.6.4. Instructions for sample collection

6.4.6.4.1. Sputum

Samples will be processed dependent on the type of analyte of interest. For assessments that do not need to be completed immediately, the processed samples will be aliquoted for storage at -80° C. Please see MOP 5 for additional details.

6.4.6.5. Measurements

The current protocol for sample processing will allow a variety of different measurements, including:

- 1) Mucin/water content including for example total mucin concentration, muc5AC and muc5B contributions to total mucins, mucus rheologic parameters, mucin complex discovery proteomics-mass spectrometry, and viscosity
- 2) Regulators of mucus water/mucin content such as nucleotides and nucleosides
- 3) Microbiology including both bacteria and viruses
- 4) Cells, for example inflammatory/respiratory epithelial cell numbers
- 5) Soluble biomarkers.

Please see discussion in other sections of the protocol for determining the markers to test in biological fluids (see Section 4.2.7) including cytokines, PGP, and discovery proteomics.

6.4.6.6. Human Subjects' Protection and Risks

6.4.6.6.1. Risks with hypertonic saline

Inhalation of hypertonic saline for sputum induction may result in wheezing, coughing, or chest tightness, particularly in susceptible individuals such as those with asthma. Asthmatic participants will be pre-medicated with albuterol in order to minimize this risk. Spirometry will be evaluated for all participants before induction as well as at prescribed intervals during each of the three levels of hypertonic saline. Participants may also experience transient throat irritation during the hypertonic saline inhalation but this generally resolves post-induction when the participant is provided with a snack and juice or water.

6.4.6.6.2. Risks with albuterol

See section 6.4.1

6.4.7. Medical History and Questionnaires

6.4.7.1. Medical History

A detailed medical history will be collected on each participant, including history of lung disease, cardiovascular disease, and cancer. Participants will be asked about their respiratory health history, including smoking status, second hand smoke exposure, as well as possible occupational and environmental exposures. Participants will also be asked to provide a medication list. The study coordinator will administer this form.

